**Table 1. Study Schedule of Assessment**

Visit Identifier' Abbreviations used in this table may be found in Section 10.11.	Screening	Baseline (Day 1)	Day 5	Day 10	Day 15	Day 21	Day 28	Day 35	Day 44	LTF/U		ET (pilot to Day 44)	Notes
										Week 12	Week 24		
Visit Window	Day -1 to Day 1	0 days	bl:1 day	bl:1 day	±2 days	±2 days	±2 days	±3 days	±3 days	±1 days	±7 days	±5 days	
 
Screening procedures may be done from Day -1 to Day 1, and may be completed on the same calendar day as Baseline/Day 1 procedures. If screening and baseline visits are conducted on the same calendar day, assessments and procedures that are listed to occur at both visits only need to be completed once.
 

Study intervention dispensation		X	X	X									
 
Study intervention will be dispensed on Day 1, Day 5, and Day 10 (see Section 6.1.1).
 
Should eGFR or eCrCl (based on the point-of-care creatinine) on Day 5 or Day 10 warrant a dose modification, replacement study intervention will be dispensed on Day 5 or Day 10. See Section 10.7.1 for age specific kidney function calculations.
 
See Section 6.6.
 

Study intervention administration		Day 1 through Day 15											
 
Baseline assessments should be performed before administration of the first study intervention, except for PK sampling.
 
The first dose of study intervention will be administered to all participants on Day 1 during the in person visit. All subsequent doses of study intervention (ie, 29) will be self-administered (or administered to the participant by a legal guardian or caregiver). If only 1 dose of study intervention is administered on Day 1, study intervention administration should end on Day 16.
 
See Section 6.1.1.
 

Study Intervention Accountability													
Retrieval of unused study intervention and empty study intervention containers			X	X	X							X	
 
If the Day 15 visit is conducted prior to last dose of study intervention, empty study intervention containers and unused study intervention should be returned at the Day 21 visit.
 
See Section 6.5.
 

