Arm Title	Nirmatrelvir/ritonavir 5-day	Nirmatrelvir/ritonavir 10-day	Nirmatrelvir/ritonavir 15-day
Arm Type	Experimental, placebo	Experimental, placebo	Experimental
Arm Description	Participants will receive nirmatrelvir/ritonavir 300 mg/100 mg (or 150 mg/100 mg for participants with eGFR $\geq 30$ to $< 60$ mL/min/1.73 m  or eCrCl $\geq 30$ to $< 60$ mL/min) q12h from Day 1 through Day 5 followed by placebo for nirmatrelvir/placebo for ritonavir q12h for Day 6 through Day 15.	Participants will receive nirmatrelvir/ritonavir 300 mg/100 mg (or 150 mg/100 mg for participants with eGFR $\geq 30$ to $< 60$ mL/min/1.73 m  or eCrCl $\geq 30$ to $< 60$ mL/min) q12h from Day 1 through Day 10 followed by placebo for nirmatrelvir/placebo for ritonavir q12h for Day 11 through Day 15.	Participants will receive nirmatrelvir/ritonavir 300 mg/100 mg (or 150 mg/100 mg for participants with eGFR $\geq 30$ to $< 60$ mL/min/1.73 m  or eCrCl $\geq 30$ to $< 60$ mL/min) q12h from Day 1 through Day 15.
Associated Intervention Labels	Nirmatrelvir/ritonavir (5-day)	Nirmatrelvir/ritonavir (10-day)	Nirmatrelvir/ritonavir (15-day)

Nirmatrelvir/ritonavir may be shipped by courier to study participants if permitted by local regulations and in accordance with storage and transportation requirements for the nirmatrelvir/ritonavir. Pfizer does not permit the shipment of nirmatrelvir/ritonavir by mail. The tracking record of shipments, including temperature monitoring data, and the chain of custody of nirmatrelvir/ritonavir must be kept in the participant's source documents/medical records.

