The proportion of participants with any severe targeted signs/symptoms attributed to COVID-19 through Day 44 will be summarized by treatment group. A participant with severe score for any targeted symptoms post-baseline will be counted as severe. Additionally, the proportion of participants reporting the presence of each targeted sign and symptom that is mild, moderate, or severe categories over time will also be presented.

In addition, to understand the severity of signs/symptoms attributed to COVID-19, the following analysis will be performed:

- 1. Proportion of participants with any severe targeted signs/symptoms attributed to COVID-19 at DAY 1 (baseline).
- 2. Proportion of participants with any severe targeted signs/symptoms attributed to COVID-19 Day 2 to end of active study treatment (during treatment; treatment arm dependent).
- 3. Proportion of participants with any severe targeted signs/symptoms attributed to COVID-19 from end of active treatment to Day 44 (post treatment).

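### SAP 6.2.17 reports severe symptoms during and after active treatment over different days in each arm, so these two rows cannot be compared between arms

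*SAP*

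**What the plan says.** SAP 6.2.17 first plans the proportion of participants with any severe targeted symptom through Day 44, by treatment group. The event rule is cumulative: "A participant with severe score for any targeted symptoms post-baseline will be counted as severe". The section also plans each symptom's severity categories over time. It then adds three summaries: Day 1; Day 2 until active drug ends, marked "during treatment; treatment arm dependent"; and "from end of active treatment to Day 44 (post treatment".

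Protocol 6.1 fixes when active drug ends:

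- 5-day arm: "q12h from Day 1 through Day 5 followed by placebo for nirmatrelvir/placebo for ritonavir q12h for Day 6 through Day 15"
- 10-day arm: "q12h from Day 1 through Day 10 followed by placebo for nirmatrelvir/placebo for ritonavir q12h for Day 11 through Day 15"
- 15-day arm: "q12h from Day 1 through Day 15"

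The schedule of activities (Protocol Table 1) allows a one-day shift: "If only 1 dose of study intervention is administered on Day 1, study intervention administration should end on Day 16".

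The SAP gives no common-window version of the split, no rate per day and no adjustment for window length. All analyses are descriptive (SAP 5.1), and SAP 5.2 presents all data by treatment group.

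**The concern.** A proportion with any severe score grows with the number of days observed. Here that number is set by the randomized factor itself. Days 6 to 15, still early in the illness, count as post-treatment in the 5-day arm and as on-treatment in the 15-day arm. Side by side, the on-treatment row would tend to make long courses look worse, and the post-treatment row would tend to make them look better.

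The second effect matters more. Protocol 4.3 justifies longer courses by the prospect of preventing a viral increase once treatment stops. Fewer severe symptoms after longer treatment is the pattern a reader will be looking for, and these windows lean towards it even when duration has no effect.

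The principle is already accepted elsewhere in the trial. Amendment 1 moved the start of the primary endpoint's sustained period from the end of active treatment to Day 15, so that follow-up would have the same length in all groups.

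**Working it through.** The documents state no day counts for these windows, so there is no planned figure to reproduce.

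**Step 1: window lengths.** Let E be the last day of active drug (5, 10 or 15, from Protocol 6.1). The on-treatment window, Day 2 to E, has E − 1 days. The post-treatment window, Day E + 1 to 44, has 44 − E days.

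| Arm | On treatment | Post treatment |
|---|---|---|
| 5-day | Day 2-5: 4 days | Day 6-44: 39 days |
| 10-day | Day 2-10: 9 days | Day 11-44: 34 days |
| 15-day | Day 2-15: 14 days | Day 16-44: 29 days |

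If the last treatment day is counted as post-treatment, those windows become 40/35/30 days. If only one dose is taken on Day 1 and each course ends a day later, the windows are 5/10/15 and 38/33/28 days. The imbalance remains either way.

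**Step 2: direction.** Day 2-5 lies inside Day 2-10, which lies inside Day 2-15. The post-treatment windows nest in reverse. Anyone severe in a shorter window is also severe in the longer one that contains it. So, if symptoms follow the same course in every arm, the expected on-treatment proportion cannot fall and the expected post-treatment proportion cannot rise as the course lengthens. This needs no model. The arms differ strictly only if some participants have their first post-baseline severe score (on-treatment row) or their last one (post-treatment row) on Day 6-15.

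**Step 3: size with daily scores.** The documents give no daily risk of a severe score, so the risks here are assumptions. With independent days, P(any severe in window) = 1 − ∏(1 − p_d).

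Take p_d = 0.06 × 0.5^((d − 2)/4) in every arm. Days 2 to 5 have risks of 6.00, 5.05, 4.24 and 3.57%, so Day 2-5 gives 1 − 0.9400 × 0.9495 × 0.9576 × 0.9643 = 17.6%. For a flat 1% daily risk the formula is 1 − 0.99^k, where k is the number of days.

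| Daily scores, identical arms | During, 5/10/15-day | Post, 5/10/15-day |
|---|---|---|
| 6% on Day 2, halving every 4 days | 17.6/26.2/29.5% | 17.3/7.6/3.3% |
| Flat 1% | 3.9/8.6/13.1% | 32.4/28.9/25.3% |

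**Step 4: size with visit scores.** Protocol Table 1 marks COVID-19 signs and symptoms at Day 1, 5, 10, 15, 21, 28, 35 and 44. On that basis the windows hold 1/2/3 assessments during and 6/5/4 after. With the same p_d at those days only:

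| Visit scores, identical arms | During, 5/10/15-day | Post, 5/10/15-day |
|---|---|---|
| 6% on Day 2, halving every 4 days | 3.6/5.0/5.6% | 2.4/0.9/0.3% |
| Flat 1% | 1.0/2.0/3.0% | 5.9/4.9/3.9% |

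**Step 5: persistence within a person.** Independent days exaggerate the on-treatment gap, because most people who are severe on Day 6-15 were probably already severe on Day 2-5. Assume daily scores, 30% of participants severe from Day 1 with an exponential duration of mean 4 days, and 8% relapsing on a day spread evenly over Day 6 to 30. Simulation gives 23.5/24.7/25.9% during and 16.0/8.7/5.5% after. The on-treatment spread is 25.9 − 23.5 = 2.4 points, against 29.5 − 17.6 = 11.9 points in step 3. The post-treatment ratio is still 16.0/5.5, about threefold.

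**Step 6: common windows.** Under the first model of step 3, Day 2-5, 6-10, 11-15 and 16-44 give 17.6, 10.5, 4.5 and 3.3% in every arm. Identical arms then look identical.

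**The case against.** The strongest reply has four parts.

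- **Common-clock analyses are already planned.** The any-severe proportion through Day 44 uses one window for all arms and is the listed secondary endpoint. By-symptom severity over time compares the same days. Both are unaffected. This stands, although neither gives the any-severe proportion by period.
- **The feature is disclosed and answers its own question.** The SAP says the window depends on the arm. Describing severity before, on and after active drug is legitimate within an arm and matches how SAP 6.2.6 anchors viral rebound. No test is planned, and between-arm differences with intervals are specified only for the primary endpoint. This also stands. Disclosure does not remove the artefact once the arms are printed side by side.
- **The large percentages need daily scores to Day 44.** SAP 6.2.17 says ratings are daily, but the protocol schedule marks symptoms only at visits, while marking the dosing log daily for Day 1-15. Protocol 8.2.1 ties diary entries to that schedule. With visit scores the gaps shrink to about 2 points. This stands for size, not direction.
- **Independent days overstate the on-treatment gap.** This stands, as step 5 shows.

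A reader might go further and infer that the severe-symptom endpoint is invalid, that the plan would report symptom rebound after short treatment where none exists, or that the two rows should be deleted. The documents do not support this: the endpoint itself uses a common window, no between-arm inference is drawn from the two rows, and they are sound as within-arm descriptions.

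**Conclusion.** The point holds as a limit on interpretation. Items 2 and 3 of SAP 6.2.17 cannot be compared between arms, because their windows differ by arm and nest in a fixed order. The direction of the artefact in expected proportions rests only on the cumulative event rule and the dosing schedule. Observed proportions will also vary by chance, with about 50 participants per arm in the main population.

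The size rests on assumptions the documents cannot settle. Across the scenarios shown, the spread between the 5-day and 15-day arms runs from about 2 points (visit scores, or persistent symptoms in the on-treatment row) to 14 points (post-treatment row, independent daily scores: 17.3 − 3.3). The post-treatment row deserves more care, since it keeps a clear gradient under persistence and points the same way as the hypothesised benefit.

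These are supplementary descriptive rows for one secondary endpoint. The primary endpoint, the through-Day-44 severe-symptom proportion and the safety analyses do not depend on them. This is a cheap improvement, not a flaw that threatens the trial's conclusions.

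**What to change.** In SAP 6.2.17:

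1. Keep items 2 and 3 as within-arm descriptions, and state in the text and table footnote that they are not for comparison between arms.
2. Add the proportion with any severe targeted symptom in windows common to all arms (Day 2-5, 6-10, 11-15 and 16-44), and name these rows as the basis for comparing arms by period. The cut-points match the planned switch days, so arms on and off drug are compared over the same days, apart from the possible one-day shift for participants who take a single dose on Day 1.
3. State whether the last day of active treatment belongs to item 2 or item 3.
4. Reconcile the SAP's daily rating with the visit-based marking in the protocol schedule. If scores exist only at visits, each of the first three windows nominally holds one assessment and should be labelled so.

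The change uses data already collected. It costs SAP wording, the derivation of four window flags and a few extra table rows.

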6.2.18. Nirmatrelvir and ritonavir PK in plasma and whole blood

Nirmatrelvir and ritonavir PK in plasma and whole blood (if feasible) will be performed and summarized by the PK/PD group.

6.2.19. Other Endpoint(s)

Not applicable for this study.

DMB02-GSOP-RF02 7.0 Statistical Analysis Plan Template 31-Jan-2022 PFIZER CONFIDENTIAL TMF Doc ID: 98.03 Page 22 of 32

6.3. Subset Analyses

Subgroup analysis will be performed for the main study population as numbers permit and results will be summarized only. Subgroup analyses of the primary endpoint will include:

- age group (<65, ≥ 65 and <18; ≥ 18);
- Sex (Male, Female);
- Race (White, Black or African American, Asian, Other);
- Ethnicity (Hispanic/Latino, Not Hispanic/Latino);
- BMI category (<25, 25-29, ≥30);
- Immunocompromised Category (stratification factor*): Participants considered immunocompromised based solely on receiving corticosteroids or TNF blockers (yes/no)
- Baseline viral load defined as: $< 10^4$ copies/mL vs $\ge 10^4$ copies/mL
- Baseline viral load defined as: $< 10^7$ copies/mL vs $\ge 10^7$ copies/mL);
- Duration since first symptom (<= 5 days, > 5 days <= 30, >30)
- Vaccination status (unvaccinated or received last vaccination more than 6 months prior to randomization vs received last vaccination within 6 months prior to randomization)
 - *: Participants will be analyzed according to the category as determined by the CRF data and not according to the category selected at randomization (when different).
 - Subgroup analysis is not planned for the population with rebound, but may be performed if numbers permit.

6.4. Baseline and Other Summaries and Analyses

6.4.1. Baseline Summaries

The demographic characteristics will be summarized by treatment group within the FAS. This will include age, sex, race, ethnicity, baseline height, baseline weight, BMI, eGFR/eCrCl, renal function category, and region. Renal function will be based on the baseline eGFR/eCrCl (mL/min/1.73 m²) using the following categories: Normal (\geq 90), Mild Impairment (\geq 60 to <90), Moderate Impairment (\geq 30 to <60), and Severe Impairment (<30).

All baseline disease characteristics, including COVID-19 disease (e.g., vaccination status, baseline serology, baseline viral load) and immunocompromised disease characteristics, will be summarized by treatment group within the FAS.

DMB02-GSOP-RF02 7.0 Statistical Analysis Plan Template 31-Jan-2022 PFIZER CONFIDENTIAL TMF Doc ID: 98.03 Page 23 of 32

6.4.2. Study Conduct and Participant Disposition

Participant evaluation groups will be presented for all enrolled participants, and participant disposition will be summarized within the FAS population. The number of participants, treated, completing, and discontinuing by study phase, as well as the number of participants in each analysis set will be summarized by treatment group. For participants who did not complete the study, the reasons for withdrawal from the study will be presented.

6.4.3. Study Treatment Exposure

Duration of treatment will be summarized within the SAS population. The duration of treatment will be calculated as follows:

Duration of treatment = Date of last dose of study drug - date of first dose of study drug +1.

Compliance over the whole treatment period will be calculated as follows:

Compliance = Actual Number of Doses Received * 100 Planned Number of Doses

A subject is considered compliant if between 80% and 120% of the planned number of doses is received. Medication compliance will be summarized by treatment group. The compliance will be summarized in the following categories: < 80%, $\ge 80\%$.

6.4.4. Concomitant Medications and Nondrug Treatments

The frequency of prior and concomitant medications will be summarized by treatment based on the WHO-drug coding dictionary within SAS population in accordance with Clinical Data Interchange Standards Consortium (CDISC) and Pfizer Standards (CaPS).

Concomitant medications of special interest will include anti-viral and mAb therapies (eg., remdesivir, dexamethasone, baricitinib, and tocilizumab). Prior medications of special interest will include molnupiravir, Evusheld, monoclonal antibodies, convalescent plasma, steroid treatment, and immunosuppressant medications (ie., medications that qualify the participant for the study).

6.5. Safety Summaries and Analyses

Standard summary tables and listings will be generated in accordance with Clinical Data Interchange Standards Consortium (CDISC) and Pfizer Standards (CaPS) for safety reporting for the following parameters: adverse events, lab parameters, vital signs, discontinuations from study, discontinuations from treatment, and treatment duration.

6.5.1. Adverse Events

It should be recognized that most studies are not designed to reliably demonstrate a causal relationship between the use of a pharmaceutical product and an adverse event or a group of adverse events. Except for select events in unique situations, studies do not employ formal adjudication procedures for the purpose of event classification. As such, safety analysis is

DMB02-GSOP-RF02 7.0 Statistical Analysis Plan Template 31-Jan-2022 PFIZER CONFIDENTIAL TMF Doc ID: 98.03 Page 24 of 32 generally considered as an exploratory analysis and its purpose is to generate hypotheses for further investigation.

All adverse events will be coded according to the Medical Dictionary for Regulatory Activities (MedDRA) and will be summarized by treatment group within SAS population.

6.5.2. Laboratory Data

Laboratory values and the corresponding changes from baseline will be summarized with descriptive statistics by treatment group over time in the SAS.

Laboratory shift tables from baseline utilizing central lab data will be presented for the following laboratory parameters at baseline: Liver function tests (ALT/AST), estimated glomerular filtration rate and Creatinine Clearance (derived using eGFR CKD EPI or Cockcroft-Gault Equation respectively), TSH, T4 (free), platelets, albumin, and total protein, and WBC.

All laboratory data will be reported in accordance with Clinical Data Interchange Standards Consortium (CDISC) and Pfizer Standards (CaPS) for safety reporting.

6.5.3. Vital Signs

The measurement taken immediately prior to start of study drug will be used as the baseline for calculating changes in vital signs. All vital sign data will be descriptively summarized by treatment group within SAS population and reported in accordance with the Pfizer Data Standards for safety reporting.

6.5.4. Electrocardiograms

Not Applicable.

7. INTERIM ANALYSES

7.1. Interim Analyses and Summaries

There is no interim analysis planned for this study.

7.2. Data Monitoring Committee

This study will use an E-DMC. The E-DMC is independent of the study team and includes only external members. The E-DMC charter describes the role of the DMC in more detail. The E-DMC will be responsible for ongoing monitoring of the safety of participants in the study according to the charter. The recommendations made by the E-DMC will be forwarded to the appropriate authorized Pfizer personnel for review and final decision. Pfizer will communicate such decisions, which may include summaries of aggregate analyses of safety data to regulatory authorities or investigators, as appropriate.

> DMB02-GSOP-RF02 7.0 Statistical Analysis Plan Template 31-Jan-2022 PFIZER CONFIDENTIAL TMF Doc ID: 98.03 Page 25 of 32

8. APPENDICES

Endpoint	Analysis Type	Population	Data Inclusion and Rules for Handling Intercurrent Events and Missing Data	Analysis Model
Proportion with sustained SARS- CoV-2 RNA < LLOQ from Day 15 to Day 44 (NP)	Primary	Evaluable, FAS	Intercurrent event: non-study anti- viral or mAb therapy – participant considered failure No imputation of missing data	Descriptive (n, %), 95% CI for proportion and the difference in proportion using binomial distribution normal approximation
Proportion with sustained SARS- CoV-2 RNA < LLOQ from Day 15 to Day 44 (NP)	Supplementary	Evaluable	Intercurrent event: non-study anti- viral or mAb therapy – data excluded/considered missing No imputation of missing data	Descriptive (n, %), 95% CI for proportion and the difference in proportion using binomial distribution normal approximation
Proportion with sustained SARS- CoV-2 RNA < LLOQ from Day 15 to Day 44 (NP)	Supplementary	Evaluable	Intercurrent event: non-study anti- viral or mAb therapy – data included as is No imputation of missing data	Descriptive (n, %),95% CI for proportion and the difference in proportion using binomial distribution normal approximation
Proportion with sustained SARS- CoV-2 RNA < LLOQ from Day 15 to Day 44 (NP)	Supplementary	Evaluable	Participants with baseline SARS- CoV-2 RNA level <lloq be
excluded Intercurrent event: non-study anti- viral or mAb therapy – participant considered failure</lloq>	Descriptive (n, %), 95% CI for proportion and the difference in proportion using binomial distribution

Appendix 1. Summary of Efficacy Analyses

DMB02-GSOP-RF02 7.0 Statistical Analysis Plan Template 31-Jan-2022 PFIZER CONFIDENTIAL TMF Doc ID: 98.03 Page 26 of 32

Endpoint	Analysis Type	Population	Data Inclusion and Rules for Handling Intercurrent Events and Missing Data	Analysis Model
			No imputation of missing data	normal approximation
Proportion with sustained SARS- CoV-2 RNA < LLOQ from Day 15 to Day 44 (NP)	Supplementary	Evaluable	Participants who do not meet the protocol-defined immunocompromised criteria will be excluded. Intercurrent event: non-study anti- viral or mAb therapy – participant considered failure No imputation of missing data	Descriptive (n, %), 95% CI for proportion and the difference in proportion using binomial distribution normal approximation
Time to first SARS- CoV-2 RNA < LLOQ (NP)	Secondary	Evaluable with BL ≥ LLOQ	No imputation for missing data	KM curves
Time to sustained SARS-CoV-2 RNA < LLOQ (NP)	Secondary	Evaluable with BL ≥ LLOQ	No imputation for missing data	KM curves
Proportion with SARS-CoV-2 RNA <lloq over="" time
(plasma)</lloq>	Secondary	Evaluable	Missing at timepoint imputed as not <lloq< td="">Descriptive (n, %)	</lloq<>	Descriptive (n, %)
Proportion with SARS-CoV-2 RNA <lloq over="" time
(NP)</lloq>	Secondary	Evaluable	Missing at timepoint imputed as not <lloq< td="">Descriptive (n, %)	</lloq<>	Descriptive (n, %)
Change from baseline in SARS- CoV-2 RNA level over time (NP & plasma)	Secondary	Evaluable	<lloq 1.7,="" as="" imputed="" post-bl
undetectable imputed as 0.0, no imputation for missing data</lloq>	Descriptive summary
Rebound in SARS- CoV-2 RNA up to Day 44 (NP) defined as a half log_{10} copies/mL increase or greater relative to EOT (active) with follow-up viral RNA level $\geq 2.5 \ log_{10}$ copies/mL	Secondary	Evaluable with EOT (active) and 1 post-EOT not missing	No imputation for missing data	Descriptive (n, %)

DMB02-GSOP-RF02 7.0 Statistical Analysis Plan Template 31-Jan-2022 PFIZER CONFIDENTIAL TMF Doc ID: 98.03 Page 27 of 32

Endpoint	Analysis Type	Population	Data Inclusion and Rules for Handling Intercurrent Events and Missing Data	Analysis Model
Rebound in SARS- CoV-2 RNA up to Day 44 (NP) defined as a half log_{10} copies/mL increase or greater relative to EOT (active) with follow-up viral RNA level \geq 3.0 log_{10} copies/mL	Secondary	Evaluable with EOT (active) and 1 post-EOT not missing	No imputation for missing data	Descriptive (n, %)
Rebound in SARS- CoV-2 RNA up to Day 28 (NP) defined as a half \log_{10} copies/mL increase or greater relative to EOT (active) with follow-up viral RNA level \geq 3.0 \log_{10} copies/mL	Secondary	Evaluable with EOT (active) and 1 post-EOT not missing	No imputation for missing data	Descriptive (n, %)
Proportion with COVID-19-related hospitalization >24 hours, or death through Day 28	Secondary	Evaluable	Max censor time at Day 28	KM method
Proportion with death (all cause) through Week 24	Secondary	FAS	Max censor time at Week 24	KM method
Proportion with COVID-19-related hospitalization	Secondary	Evaluable	Max censor time at Day 44	KM method
Proportion with COVID-19-related ICU admission	Secondary	Evaluable	Max censor time at Day 44	KM method
Proportion requiring IMV or ECMO	Secondary	Evaluable	Max censor time at Day 44	KM method
Number of days in hospital and ICU stay	Secondary	Evaluable, participants with COVID- 19-related hospitalizat ion	In the absence of a specific record of a COVID-19-related hospitalization, participants will be considered to be out of hospital	Descriptive summary

DMB02-GSOP-RF02 7.0 Statistical Analysis Plan Template 31-Jan-2022 PFIZER CONFIDENTIAL TMF Doc ID: 98.03 Page 28 of 32

Endpoint	Analysis Type	Population	Data Inclusion and Rules for Handling Intercurrent Events and Missing Data	Analysis Model
Number of COVID- 19-related medical visits through Day 44 and through Week 24	Secondary	Evaluable	In the absence of a specific record of a COVID-19-related medical visit, participants will be considered to not have a COVID- 19-related medical visit.	Descriptive summary
Duration of each targeted COVID-19 signs/symptoms	Secondary	Evaluable	No imputation for missing data	KM method
Proportion with severe signs/symptoms attributed to COVID-19	Secondary	Evaluable	No imputation for missing data	Descriptive (n, %)

